### 3.1. Sequential design

Sequential design is a pivotal element of the adaptive strategy that allows for assessing participants data while the trial is ongoing for optimizing trial performance. In this study, we include a 3-stage procedure with two homogeneous interim analyses and one final analysis (K=3). Sequential design is always associated with inflation of statistical error due to multiple comparisons on the same accrued set of data. To control for this bias, we have defined ad hoc statistical plan and define adequate error spending function. When the sample size expected for each interim analysis is reached, patients will continue to be enrolled and randomized until either the results of that interim analysis will be available or the minimum sample size expected for the subsequent stage will be reached.

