## 5. Study procedure

### 5.1. Assignment of interventions

Randomization will be centralized and coordinated by the University of Trieste. The randomization list will be generated by a study statistician with Stata 14.2 using block randomization. The list will be implemented in the REDCap® randomization module, which allows centralized allocation of patients through the REDCap® web platform and grants allocation concealment. In each participating center the clinician in charge of the randomization will have secure access to the REDCap® web platform and, after checking whether the study inclusion and exclusion criteria are met, will automatically receive the assignment arm for the enrolled patient. This is an open-label trial, therefore, both the clinician and the patient will be aware of the assigned treatment.

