### 5.2. Data collection and management

A clinical database using REDCap® trial data management system will be developed with a web hosting facility. Electronic case report forms (eCRFs) will be developed to collect all clinical and laboratory related information. The trial database will include baseline information, information on demographics (age, gender), underlying illnesses, baseline and follow-up clinical and laboratory data for the purpose of assessment of clinical outcome. All data queries and corrections will be jointly conducted by the study team prior to database lock. The study team at the University of Trieste, Centro di Riferimento Oncologico of Aviano, and the Institute for Infectious Diseases “L. Spallanzani” of Rome will manage the data and will conduct quality control of the data. All analyses performed, the Clinical Study Report(s) and the final data set will be archived together according to the standard operating procedures and the guidelines of the University Hospital of Cattinara.

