## 6.2. Sample size

Minimum and maximum sample size will significantly change according to the observed effect within the trial sample (expected **average** sample size is between 200 and 680 participants, figure 2). In particular, we expect to enroll 100 participants per arm at the first stage and then between 15 and 175 per arm for each eventual stage if the stopping rules were not met. The actual number of new participants in each arm will be calculated according to the maximum likelihood estimates on observed efficacy at each interim analysis with an overall conditional power for next stage equal to 90%. This approach allows either to minimize the number of enrolled participants if the experimental hypothesis is too conservative or to have a good power level if the experimental hypothesis is too optimistic. The average sample size with relative power and the overall probability for meeting stopping rules according to different level of efficacy of arm 1 vs. arm 2 are reported in figure 2 and figure 3, respectively.

	$H_0: \pi_T - \pi_C = 0$			
Critical values	Stage 1	Stage 2	Stage 3	
Reject H0 (Efficacy)	3.421	2.419	1.975	1.975
Accept H0 (Futility)	-0.695	1.002	1.975	1.975
Information rate	0.333	0.667	1	1
alpha spent	0.0003	0.0079	0.025	0.025

*Table 1 Preplanned critical values (Fisher test) for application of early stopping rules*

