### 6.3. Analysis of efficacy (primary outcome)

Interim analyses and final analysis will be carried out by taking into account the potential effect of each individual component of the adaptive design. The interim analyses will provide:

- a) estimate of efficacy as risk difference and relative 95% CI
- b) criteria for stopping rules
- c) if the stopping rules are not met the analysis will provide the number of participants to be randomized for the subsequent stage in each arm.
- d) final analysis will provide efficacy as difference estimate of efficacy as risk difference and relative 95% CI

Subgroup analyses will be carried out if the sample size will allow to. In this case, the following groups will be taken into consideration:

- a) Patients requiring only oxygen therapy, either low-flow or high-flow (HFNC) during the study period
- b) Patients requiring only low-flow oxygen therapy during the study period;

- c) Patients requiring high-flow oxygen therapy (HFNC) but not ventilatory support during the study period
- d) Patients requiring mechanical ventilation, either invasive or noninvasive during the study period
- e) Patients requiring noninvasive mechanical ventilation but not invasive mechanical ventilation during the study period
- f) Patients requiring invasive mechanical ventilation during the study period.

All the analyses will be conducted by the trial statisticians following the intention-to-treat principle.

In case of deviations from the study protocol, such as cross-over between arms, sensitivity analysis will be carried out (eg., *per protocol* analysis).

[figure not shown]

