## 7.3. Safety Monitoring Plan

A DSMB will be established, comprising four independent physicians with statistical support provided to them by the Institute for Infectious Diseases “L. Spallanzani”. The trial statisticians will provide details of safety outcomes and any significant differences in primary outcomes according to treatment arm to the DSMB at any scheduled interim analysis. The stopping rule will be a statistically significant difference in primary outcomes between the two arms. The interim analysis results will be communicated to the trial team along with the DSMB recommendations for action. If there is a significant safety concern will be raised, the DSMB may recommend to the Principal Investigator that the trial should be stopped.

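### Section 7.3 sends comparative interim results, not only the DSMB recommendation, to the trial team of an open-label trial that goes on recruiting

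*Protocol*

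**What the plan says.** On release, protocol section 7.3 says: "The interim analysis results will be communicated to the trial team along with the DSMB recommendations for action". The same section has the trial statisticians give safety outcomes and "any significant differences in primary outcomes according to treatment arm to the DSMB at any scheduled interim analysis".

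On content, section 6.3 lists among the interim outputs an "estimate of efficacy as risk difference and relative 95% CI", the criteria for the stopping rules, and a stage size: "if the stopping rules are not met the analysis will provide the number of participants to be randomized for the subsequent stage in each arm". Section 6.1 calls the recalculation unblinded. Under section 6.2 the new number per arm, between 15 and 175, is "calculated according to the maximum likelihood estimates on observed efficacy at each interim analysis", with 90% conditional power for the next stage.

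On setting, section 5.1 says: "This is an open-label trial, therefore, both the clinician and the patient will be aware of the assigned treatment". Section 3.1 keeps recruitment open around each look: "patients will continue to be enrolled and randomized until either the results of that interim analysis will be available", or until the next stage's minimum size is reached. Section 4.4 allows additional therapies, and section 6.3 foresees cross-over between arms.

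On roles, section 5.2 lists three units of the study team, including the institute that section 7.3 names as statistical support to the DSMB, and says that they "will manage the data and will conduct quality control of the data".

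**The concern.** The release sentence covers results as well as the recommendation, and those results show which arm leads and by how much. In an open-label trial, someone who knows both a patient's arm and the leading arm has the means to act on it: whom to approach, what to add, whether to cross over, when to escalate support or discharge.

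If conduct changes after a look, later stages may estimate a different effect from stage 1. The multiplicity machinery does not reach this. Alpha spending accounts for repeated testing, and a combination test accounts for data-driven re-sizing. Both assume that looking at the data leaves the conduct of the trial unchanged.

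The outcomes most exposed are those that follow clinicians' decisions: days free from mechanical ventilation, tracheostomy, hospital days and the WHO scale, all secondary in section 4.5.

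**Working it through.** **1. The boundaries themselves are sound.** Table 1 gives efficacy bounds 3.421, 2.419 and 1.975, binding futility bounds -0.695 and 1.002, and information rates 1/3, 2/3 and 1. The efficacy bounds have the O'Brien-Fleming shape: 1.975 × √3 = 3.421 and 1.975 × √1.5 = 2.419. Integrating the crossing probabilities under no effect, with binding futility, gives cumulative alpha of 0.0003, 0.0079 and 0.0250, as Table 1 states. The problem is therefore conduct and not the alpha arithmetic.

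**2. What each kind of message discloses at interim 1.** A bare message to continue says only that -0.695 < Z < 3.421. With 100 per arm and an assumed pooled survival of 82% (midway between 77% and 87%), the standard error is √(2 × 0.82 × 0.18 / 100) = 0.0543. The message then covers risk differences from -0.695 × 0.0543 = -3.8 points to 3.421 × 0.0543 = +18.6 points. The release in section 7.3 gives the point estimate and interval instead.

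**3. What the stage size alone discloses.** The protocol gives no re-sizing formula beyond 90% conditional power at the observed effect, so this step *assumes* an equal-weight inverse-normal combination.
- Rejection at stage 2 needs (z1 + z2)/√2 ≥ 2.419, so z2 ≥ 3.421 - z1.
- At the observed effect, z2 has mean z1 × √(n2/100). Setting conditional power to 90% gives n2 = 100 × ((3.421 + 1.2816 - z1)/z1)² per arm.
- z1 = 2.02 gives 176, z1 = 2.5 gives 78, and z1 = 3.0 gives 32. A size below the 175 cap thus implies z1 above about 2.0.

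Share of continuing trials with a stage-2 size below the cap, control survival 77%:

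| True effect | Fisher p-value converted to Z | Normal approximation |
|---|---|---|
| 10 points | about 34% | about 40-41% |
| 5 points | about 10% | about 13% |
| none | about 2% | about 3% |

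Section 6.1 names Fisher's exact test, so the Fisher column is closer to the plan. In most continuing trials under these scenarios the size would sit at the cap and convey only a broad range. This leak is secondary in any case, because section 7.3 releases the results themselves.

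**4. What changed conduct could do to the primary test.** The documents give no size for such a change, so the shifts below are *assumed* and show a range. True effect nil, survival 77%, Table 1 bounds, equal stage weights, with apparent methylprednisolone survival shifted only after interim 1:

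| Assumed shift (points) | Type I error, 100 per arm in later stages | 175 per arm in later stages |
|---|---|---|
| 0 | 2.5% | 2.5% |
| 1 | 3.8% | 4.3% |
| 2 | 5.6% | 7.0% |
| 3 | 8.0% | 11% |
| 5 | 15% | 23% |

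**The case against.** The strongest reply has four parts.

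- **Recipients.** A reader might infer that results go to the bedside clinicians. The text does not say so. The trial team is not defined in section 7.3, section 8.2 says the study team is not in overall control of care, and section 7.1 separates investigators from treating teams. Section 1, on the management committee, is not in the text available here and may define the term. This stands as a limit on the claim. It does not remove it: in section 5.1 a clinician at each centre performs the randomisation, so overlap is plausible, and nothing in the text shown restricts the recipients.
- **Primary outcome.** Death by day 28 is objective, allocation is concealed through a central platform, and analysis is by intention to treat. This stands against biased ascertainment or subverted allocation. It does not stop differential co-treatment, cross-over or selective approach of patients.
- **Stage size.** A reader might infer that the announced size always gives the effect away. It does not. Below the cap it is informative, but under the stated assumption most continuing trials would announce the cap.
- **Shared institute.** Sections 5.2 and 7.3 name the same institute in two roles. A reader might infer that the same people hold both. The text does not say that, and internal separation is commonly set out in a DSMB charter.

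The point is not an item merely left to a charter or analysis plan. Section 7.3 states positively that results are released, and a later document that withheld them would contradict it.

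**Conclusion.** The concern holds as a stated rule that exposes the trial to operational bias and should be changed before the first interim, since a release cannot be undone. It rests on three things in the text: results are released along with the recommendation, those results are comparative by arm, and an open-label trial goes on recruiting.

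It is a risk and not a demonstrated bias, because it depends on people acting on what they learn. It is greatest for the clinician-driven secondary outcomes and smaller, but not nil, for 28-day survival. Its size cannot be derived from the protocol. The type I error range rests on assumed shifts, and the stage-size figures rest on an assumed equal-weight inverse-normal combination. No boundary, alpha or sample-size figure in the plan is wrong on this account.

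**What to change.** Replace the release sentence in section 7.3 with:

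> Only the DSMB recommendation (stop or continue) and an operational recruitment target are communicated to the trial team and the investigators; comparative interim results and the sample-size calculation remain with the DSMB and the statistician who runs the interim analysis until the trial ends.

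Add that this statistician takes no part in enrolment, patient care or data queries. This also settles the shared-institute question without moving any unit's work.

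Announce continuation to sites as up to 175 more per arm. The DSMB and its statistician hold the exact number and tell the team when recruitment to the stage is complete. The number should not be hidden in the randomisation module: the University of Trieste coordinates randomisation (section 5.1) and belongs to the study team (section 5.2), so it would sit with the group meant not to know it.

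The cost is protocol wording and the naming of a separated statistician. The trial team must plan for the maximum stage size. One leak remains: when stage 2 closes below the cap, its size becomes known and says something about stage 1. That is later and much less than what the present sentence releases.

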## 8. Ethical considerations

### 8.1. Research ethics approval

The trial will not commence until a Clinical Trial Authorization (CTA) is obtained from the National Ethics Committee and the local Ethics Committee for the Coordinating Centre (University Hospital of Cattinara). The protocol and trial conduct will comply with the Declaration of Helsinki (last revision, Fortaleza 2013), the Good Clinical Practice (ICH E6 Guideline for Good Clinical Practice, 1996), Italian laws and European Regulations. Ethics Committee and regulatory authorities will be informed of all subsequent protocol amendments and administrative changes, in accordance with local legal requirements

### 8.2. Informed Consent

The study team representative will approach the patient at the bedside. All co-investigators will be allowed to obtain informed consent from subjects. Patients will be given adequate time to consider their options. Although patients may still be unwell at the time of recruitment, informed consent will only be obtained if it is judged that the patient has capacity to make an informed choice. It will be made clear to patients that the study team are not in overall control of their clinical care, which will in no way be affected by their refusal to participate. The person taking consent will not exert undue influence or coerce potential recruits - this will be reinforced to team members by the PI and co-investigators. Patients will be given every opportunity to reverse their decision to enrol in the study. For non-Italian speakers, qualified translators will be provided as per local hospital protocols. For non-literate subjects, an impartial witness will be asked to certify in writing that the study has been explained in language that the subject understands and that he/she has agreed to participate in the study. Cognitively-impaired patients are excluded from this trial according to exclusion criteria. Patients should be offered the chance to receive a written summary of the trial after completion and publication should they wish – if so, a record of the contact details will be kept for this purpose.

### 8.3. Confidentiality of data and patient records

Study data will be collected and treated in accordance with the European Regulation for data protection no. 679/2016 (General Data Protection Regulation - GDPR) and Italian laws (d.lgs. 101/2018 and d.lgs. 196/2003). An anonymous identification code (i.e., progressive number) will be automatically assigned through the REDCap® web platform to any patient at enrollment and will be reported in the case report form (CRF). Encrypted transmission of data will be granted by the use of the REDCap® web platform. All study findings and documents will be regarded as confidential. The investigators and other study personnel must not disclose such information without prior written approval from the Principal Investigator. Subject confidentiality will be strictly maintained to the

extent possible under the law and local hospital policy. Identifiable information will be removed from any published data.

#### 8.4. Publications

The data obtained from all participating sites will be pooled and analyzed together as soon as possible after trial completion. Individual researchers will not publish data from the trial until the main study publication has been released.

#### 8.5. Retention of trial documents

Any electronic data records will be password-protected and stored on a server of the Coordinating Center. The PI will keep any paper-based records, study files or source documentation in a locked cabinet within the department. These records, electronic and physical, will be kept for a minimum of 10 years after the completion of the trial before being destroyed or erased. These documents will be retained for a longer period if required by the applicable regulatory requirements or institutional policy.

